The acoustic environment in the NICU is radically different from that experienced in the womb. Incubators, ventilators and cardiorespiratory monitors all contain high frequency auditory alarms specifically designed to optimally alert NICU caregivers to critical changes in infant conditions, and they do so with astounding frequency. In fact, the concept of caregiver "monitor fatigue" has entered the NICU lexicon and is the subject of current quality assurance efforts by the Vermont-Oxford Neonatal Network and others.⁷ These adverse stimuli have been shown to increase markers of neonatal stress, interfere with evolving normal sleep patterns and potentially contribute to auditory and neurodevelopmental deficits.⁴

As neonatal clinicians have become aware of the potential adverse effects of noise in the NICU, multiple interventions have been proposed in the past to deal with this issue. Acoustic monitors, visually alerting staff to high levels of noise in the NICU, have been trialed with limited success.⁸ Ear plugs have been proposed and abandoned as ineffective and problematic, given the anatomy of the neonatal auditory canal and the non-frequency selective nature of their noise

diminution.⁹ A commercially available ear muff, the “MiniMuff” has been utilized on a short term basis, but the adhesive used to fix the appliance to the skin can rapidly lead to skin irritation, prompting the manufacturer’s recommendation to limit the use of the device to a maximum period of 24 hours.¹⁰ Another approach to this problem has been the multi-million dollar redesign of NICU’s throughout the country, in order to provide single patient rooms. There is controversial evidence that such an approach leads to an increase, rather than a decrease in neurodevelopmental delays, potentially related to relative “sensory deprivation”.¹¹ None of the previous proposed solutions to this issue have been shown to be practical and/or effective.

Methods

Our proposed study is a phased pilot study to evaluate patient tolerance and nursing ease-of-use of a novel hearing protection device to reduce exposure to excessive noise among patients undergoing neonatal intensive care. The study device has been engineered by NEATCAP, LLC, to provide a circumaural hearing protector (“ear muff”) with a “low pass” filtering of sound, preferentially blocking high frequency sounds while transmitting low frequency sounds such as a mother’s voice.^{FIG 2}

The device employs a soft neoprene/nylon headband to fix the ear covers in place, with multiple sizes of both the ear covers and headbands to accommodate multiple sizes of infants.^{FIG 3} A patent for the device is pending. Recent Food and Drug Administration rulings have waived a requirement for an Investigational Device Exemption (“IDE”) for this type of device (see attached letter).

FIG 3. NEATCAP prototype noise protection device on premature infant model. illustrating circumaural ear covers. fabric band and

Phase 1 of the study will entail a 60-minute initial size and fit evaluation of the device on a

convenience sample of 25 infants admitted to the NICU. The inclusion criteria for the study include study initiation during the first two (2) weeks of NICU hospitalization and written signed informed consent from the parents of the study subjects. Exclusion criteria will include: age less than 12 hours, significant cranial trauma noted on admission, congenital anomalies of the head and/or neck, hemodynamic instability requiring pharmacologic intervention and a recommendation by the attending neonatologist not to enroll the patient for any reason.

In Phase 1, the device will be applied by a single trained senior neonatal intensive care nurse with experience in recognizing distress in NICU patients. Once proper fit of the device has been assured, it will be removed and a 30 minute “time out” interval will be employed. Baseline vital signs will then be obtained (see attached data collection sheet), the device will be re-applied and repeat vital signs will be obtained at 30- and 60-minute time periods. The device will be removed after 60 minutes and a fourth set of vital signs will be obtained 30 minutes after device removal. The primary endpoint of the study will be the absence of any device-related adverse events, including evidence of skin discomfort or irritation at the site of device application, or significant sustained changes in vital signs consistent with a stress response, as outlined in Table #1.

Table #1.


Significant elevated stress is defined as persistence of any of the following in the absence of intrusive manipulations of the patient (e.g.: IV insertions, nursing care procedures, etc.) based on the Cries Score for Pain Assessment:¹²
 
• Temperature: >0.6°F increase in temperature above baseline.• Respiration: > 20% increase in respirations per minute above baseline• Pulse: >20% increase in beats per minute above baseline• Blood pressure: >20 mm Hg increase in systolic blood pressure above baseline• Oximetry level: >5% pulse oximeter decrease below baseline	
Secondary endpoints will include NEATCAP sizing options able to fit >90% of the target population and a >80% positive response to a multi-question ease-of-use questionnaire completed by the participating NICU staff (see the attached questionnaire). The data will be stored by the Study Coordinator

--	--

and will undergo statistical analysis for repeated measures by [name], MS, with subsequent review by the primary investigator and the device consultants. If no specific negative findings are identified, Phase 2 will begin.

Phase 2 will entail a 3-day evaluation of tolerance of the device, entailing a total of three (3) eight-hour-long sessions of device use on three (3) consecutive days. The study population will consist of a convenience sample of 25 neonates with identical inclusion and exclusion criteria as outlined for Phase 1. After obtaining baseline vital signs prior to each session, the bedside NICU nurse assigned to the patient will apply the device under the supervision of the data collection RN. Temperature and blood pressure data will be obtained at 3 and 6 hours of device use and heart rate, respiratory rate and oxygen saturation levels will be recorded every hour. The device will be removed after eight hours, with continued monitoring of vital signs for another eight hours after device removal. The primary endpoint of the study will be the absence of device-related adverse events, including evidence of skin discomfort or irritation at the site of device application, or sustained changes in vital signs consistent with a stress response, as outlined in Table #1. Secondary endpoints will include a >80% positive

response to a multi-question ease-of-use questionnaire by the bedside nurse assigned to the patient and acceptance of the device by the patient's parents, by direct questioning by the principal investigator. Data for Phase 2 will be stored by the Study Coordinator with statistical analysis for repeated measures by [name], MS. All data will be de-identified by the Study Coordinator prior to analysis.

Risks/Benefits

The potential study risks to subjects include skin discomfort, irritation or pain at the site of device application and/or adverse changes in vital signs associated with device usage. The potential study benefits are to provide critical data for the product development of an optimally-designed circumaural hearing protection device for patients receiving neonatal intensive care. This pilot study will potentially lead to a trial of sustained use of this device in the NICU.

References

3. NICHD Neonatal Research Network (NRN): Extremely Preterm Birth Outcome Data. http://www.nichd.nih.gov/about/org/der/banches/ppd/programs/epbo/pages/epbo_case.aspx?start=17;31;31.

8. Liu, W. (2012). The impact of a noise reduction quality improvement project upon sound levels in the open-unit-design neonatal intensive care unit. *Journal of Perinatology*, 30, 489-496.

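### Both phases enrol 25 infants by an unspecified convenience process, with no visible count of those vetoed or not approached; admission-order enrolment with a log is a cheap improvement

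*Combined protocol and SAP*

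**What the plan says.** All of this is in the Methods of the combined protocol and SAP.

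- **Phase 1 sample:** a "convenience sample of 25 infants admitted to the NICU".
- **Inclusion:** "study initiation during the first two (2) weeks of NICU hospitalization and written signed informed consent from the parents".
- **Exclusion:** one criterion removes unstable infants by a stated rule, "hemodynamic instability requiring pharmacologic intervention". Another is open-ended: "a recommendation by the attending neonatologist not to enroll the patient for any reason".
- **Phase 2 sample:** a "convenience sample of 25 neonates with identical inclusion and exclusion criteria as outlined for Phase 1", so the open-ended exclusion carries over.
- **Primary endpoint:** in Phase 1, "The primary endpoint of the study will be the absence of any device-related adverse events"; in Phase 2, "The primary endpoint of the study will be the absence of device-related adverse events". Neither phase describes a control group.

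The text does not name who selects the convenience sample or on what basis. It describes no consecutive approach, no stratification, no screening log and no record of why an infant was vetoed. The Phase 1 data collection sheet is cited as an attachment and is not among the material available, so a log there cannot be ruled out.

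**The concern.** In a randomised comparison, selective enrolment mainly limits how far the result can be generalised. Here there is no comparator, and the event count among the enrolled infants is itself the result. The mix of infants therefore acts on the primary endpoint directly.

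Two uncounted steps lie between the eligible infants and the 25 enrolled: the attending's veto, and whatever process decides which remaining infants are approached. If either step tends to leave out infants who would react to the device, the count falls and nothing in the visible text would show it.

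The count matters for later decisions. Phase 2, with three eight-hour sessions, follows a review of the Phase 1 findings by the investigator and the device consultants. The Risks/Benefits section looks ahead to a trial of sustained use. Because Phase 2 infants are picked after that review, an unspecified choice could also be influenced by reactions already seen.

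**Working it through.** **No plan figure to reproduce.** The documents give 25 infants per phase, but no expected event rate, error rate, power or derivation of the sample size. What follows is a sensitivity illustration. Only n = 25 and the no-event endpoint come from the documents; every rate is assumed.

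**Model.** Let a share h of eligible infants be fragile with event risk a, and let the others have risk b. If a fraction v of the fragile infants is not enrolled, the fragile share among those enrolled is

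h' = h(1 − v) / (1 − hv),

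the mean event rate is p = h'a + (1 − h')b, and the chance of no event in 25 is P0 = (1 − p)^25.

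**Worked example** (h = 0.30, a = 0.20, b = 0.03):

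- No selection: p = 0.30 × 0.20 + 0.70 × 0.03 = 0.081; P0 = 0.919^25 = 0.121.
- Half the fragile infants missing: h' = 0.15/0.85 = 0.176; p = 0.060; P0 = 0.940^25 = 0.213.
- All missing: p = 0.03; P0 = 0.970^25 = 0.467.
- Selection the other way, fragile share raised to 50%: p = 0.50 × 0.20 + 0.50 × 0.03 = 0.115; P0 = 0.885^25 = 0.047.

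**Range over three assumed pairs of risks**, all with h = 30%. Each cell gives the mean rate, then P0.

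| Fragile share among enrolled | Risks 25% / 5% | Risks 20% / 3% | Risks 15% / 3% |
|---|---|---|---|
| 30% (no selection) | 11.0%; 5.4% | 8.1%; 12.1% | 6.6%; 18.1% |
| 17.6% (half missing) | 8.5%; 10.8% | 6.0%; 21.3% | 5.1%; 26.9% |
| 0% (all missing) | 5.0%; 27.7% | 3.0%; 46.7% | 3.0%; 46.7% |
| 50% (over-represented) | 15.0%; 1.7% | 11.5%; 4.7% | 9.0%; 9.5% |

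Missing half the fragile infants multiplies P0 by about 2.0 (10.8/5.4), 1.8 (21.3/12.1) and 1.5 (26.9/18.1). Over-representation moves it the opposite way.

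**What a clean result could exclude.** With 0 of 25 events, the exact one-sided 95% upper bound on the event rate is 1 − 0.05^(1/25) = 11.3%. It applies only to infants like those enrolled.

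**What the fix could recover.** The veto stays, so some fragile infants would still be excluded. Suppose the veto removes half of them and the convenience process loses the other half. At 20%/3% risks, admission-order enrolment would then move P0 from 46.7% to 21.3%, not to 12.1%. The gap between the no-selection row and the rows with fragile infants missing is therefore an upper limit on what the fix would change.

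**The case against.** A reader might infer three stronger things that the documents do not support.

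- *That systematic enrolment was given up.* None was planned; both phases openly declare convenience samples.
- *That staff choose the infants at their discretion.* The selector is not named. The only discretion stated is the attending's veto, which can exclude but cannot select.
- *That the endpoint leans toward success.* This is an inference. The veto plausibly removes fragile infants, but it may be rarely used, and convenience sampling can shift risk either way, as the last row of the table shows.

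Further points on the other side carry weight. This is a declared pilot, and Phase 1 is a 60-minute size and fit evaluation, where convenience sampling is ordinary. Table #1 defines stress events as persistent changes from each infant's own baseline, apart from intrusive handling, so fragility alone does not produce an event and a large risk gap is not self-evident. The start of Phase 2 depends on the absence of specific negative findings, with no numeric threshold, so P0 is not the probability of proceeding. The veto is also a reasonable protection for a vulnerable population and is not in dispute.

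These points remove any claim of demonstrated bias. They do not remove the structural one: in a single-arm study with a no-event endpoint, enrolment is unspecified and, in the visible text, uncounted. The pilot label does not answer this, because the remedy is on a pilot's scale. Infants who are never logged cannot be counted reliably afterwards.

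**Conclusion.** The point holds as a cheap improvement, not as an error that invalidates the plan. Enrolment in both phases follows an unspecified convenience process after an open-ended veto, and the visible text provides no count of eligible infants who are vetoed or not approached. Selective enrolment could therefore bias the tolerance result of either phase. The documents do not settle the direction; if fragile infants are passed over, a clean result becomes more likely.

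The size cannot be estimated from the documents. In the assumed scenarios, losing half the fragile infants raises the chance of 0 of 25 by a factor of about 1.5 to 2.0, and over-representing them lowers it. The conclusion rests on there being no enrolment log in the attachment that is not shown.

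**What to change.** In both phases:

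1. Replace the convenience sample with the next 25 eligible infants, approached in order of NICU admission on days when the study nurse is on duty.
2. Keep the attending veto unchanged, but record it with a coded reason before the parents are approached.
3. Report, by phase, the numbers eligible, vetoed, approached, declined and enrolled.
4. State the tolerance conclusion for non-vetoed infants like those enrolled.

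The cost is about one sentence per phase and a one-page enrolment list, with no extra staff, procedures or patients. The downsides are a few more approaches to parents and possibly slower accrual. Sampling would still be limited to duty days, and admission order does not guarantee that 25 infants cover the range of sizes needed for the Phase 1 fit endpoint of more than 90%.

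### Does having one senior nurse apply the device in Phase 1 undermine that phase's ease-of-use criterion?

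*Combined protocol and SAP*

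**What the plan says.** The Methods section introduces the work as "a phased pilot study to evaluate patient tolerance and nursing ease-of-use of a novel hearing protection device". Ease of use for nurses is therefore an aim of the two phases taken together.

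**Phase 1.** The purpose is stated as follows: "Phase 1 of the study will entail a 60-minute initial size and fit evaluation of the device". It enrols a convenience sample of 25 infants. On application, the text says "the device will be applied by a single trained senior neonatal intensive care nurse with experience in recognizing distress in NICU patients". After a pause and baseline readings, "the device will be re-applied and repeat vital signs will be obtained at 30- and 60-minute time periods", and then "The device will be removed after 60 minutes". Neither of these two later steps names who carries it out. One of the secondary endpoints, given beside Table #1, is "a >80% positive response to a multi-question ease-of-use questionnaire completed by the participating NICU staff", with a reference to an attached form. The rule for moving on is "If no specific negative findings are identified, Phase 2 will begin".

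**Phase 2.** A further 25 neonates have "a total of three (3) eight-hour-long sessions of device use on three (3) consecutive days". Here the infant's own bedside nurse puts the device on, supervised by a research nurse, and completes an ease-of-use questionnaire judged against the same threshold of more than 80%.

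**The concern.** Ease of use is a property of the device in the hands of its users, so the sampling unit for application is the nurse. If one nurse fits all 25 infants, Phase 1 samples one user. Repeating the rating over infants shows how fit and handling vary between infants, but says nothing about variation between nurses. The chosen nurse is also trained and senior, hence not a typical user.

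A numerical pass mark invites over-reading. A report that Phase 1 exceeded 80% could be taken as evidence that NICU nurses in general find the device easy to apply, when it might reflect one person's opinion. Since the Risks/Benefits section says that the study will feed product development, such a misreading could carry forward.

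**Working it through.** The plan gives no sample-size derivation, confidence level or test for ease of use, so there is no stated figure to reproduce. The check has three steps.

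**1. Is one applier the right reading?** The Phase 1 sentence speaks of a single nurse, while Phase 2 hands application to each infant's bedside nurse. The contrast supports one nurse for the whole of Phase 1. It is not certain, because re-application and removal name nobody. The questionnaire respondents are described in wider terms than one nurse, so other staff may also answer. They could rate handling and care around the device, but not application if they did not apply it. The application and questionnaire statements can both be followed, so there is no contradiction.

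**2. How large could the effect be?** This needs assumptions that are not in the documents: the applier alone answers, there is one form per infant (25 forms), and ratings by the same nurse have an intraclass correlation (ICC) between 0.1 and 0.5.

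- Pass mark: 20/25 = 80% exactly, so more than 80% needs at least 21/25 = 84%.
- Effective number of forms for nurses in general = 25 / (1 + 24 x ICC):
  - ICC 0.1: 25/3.4 = 7.4
  - ICC 0.3: 25/8.2 = 3.0
  - ICC 0.5: 25/13 = 1.9
- Probability of 21 or more out of 25, by true positive rate p among nurses. The one-nurse columns use a beta-binomial with a = p(1 - ICC)/ICC and b = (1 - p)(1 - ICC)/ICC; the last column is binomial:

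| p | One nurse, ICC 0.1 | ICC 0.3 | ICC 0.5 | 25 different nurses |
|---|---|---|---|---|
| 0.6 | 0.115 | 0.281 | 0.394 | 0.0095 |
| 0.7 | 0.270 | 0.427 | 0.522 | 0.0905 |

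So, on these assumptions, passing Phase 1 is weak evidence about nurses at large. The table also treats the nurse as a random draw, although she or he is selected for training and seniority. With a questionnaire of several items, the 80% may count items, forms or people, so 21/25 is itself only one reading. The table shows the direction of the problem and does not measure it.

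Even 25 independent answers would be imprecise: 21/25 has an exact 95% interval of 63.9% to 95.5%. The pass mark can only be a descriptive benchmark in a pilot of this size.

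**3. What depends on the Phase 1 percentage?**

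- *Primary endpoint.* Device-related adverse events and vital-sign changes. It does not use the questionnaire.
- *Progression.* The rule asks for an absence of negative findings and has no numerical link to 80%.
- *Ease-of-use conclusion for nurses.* Phase 2 supplies the data: bedside nurses both apply and rate, over at most 25 x 3 = 75 sessions if all are completed.
- *If Phase 2 does not start.* Phase 1 would be the only source, but the reason would be a negative finding about the device, and no general claim about ease of application would then be in prospect.

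**The case for a change.** The strongest case for a change is that the protocol attaches a pass mark to a measure that, for application, rests on one person, and that this is cheap to mend. The Phase 1 threshold could be dropped, the result reported as feedback from the applier, the 80% judged in Phase 2 only, and nurse codes added so that repeated forms from one nurse can be allowed for.

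Part of this stands. One applier cannot reveal differences between nurses, and the text does not say who answers in Phase 1 or what the percentage is taken over. Phase 2 is not a perfect remedy either: application is supervised, and the number of distinct nurses is not stated.

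The rest does not require a change. The Phase 1 endpoint asks for a favourable response from the staff who took part, and does not extend this to other nurses; the wider target has to be read into it. A single experienced applier also has a purpose, since it keeps application consistent while fit and early tolerance are assessed. Removing the threshold is then a matter of preference. Nurse codes and clustered intervals in Phase 2 address another question, repeated ratings by the same nurse, and would correct no interval or test that the plan specifies.

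**Conclusion.** The observation is right, but it does not call for an amendment. Phase 1 cannot describe how nurses in general manage the device, and the plan does not ask it to. The staged design leaves that to Phase 2, with the appropriate users and the same threshold, and neither the progression rule nor the safety endpoint turns on the Phase 1 percentage.

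What is left is a gap in wording about respondents and denominator. The attached questionnaire may already fill it. If not, a competent analyst would state who answered, show the applier's ratings apart from those of other staff, and draw conclusions about bedside nurses from Phase 2. The consequence is limited to the label on one secondary result in a pilot.

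This conclusion assumes that one nurse applies the device throughout Phase 1 and that Phase 2 is run as written. It does not rest on the illustrative probabilities, whose inputs (respondent, forms per infant, ICC and true rate) are not in the documents.

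### In Phase 1 both on-device changes are measured from one baseline reading, so its error produces false stress events that the persistence condition only partly removes

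*Combined protocol and SAP*

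**What the plan says.** Under Methods, Phase 1, the device is fitted, removed for 30 minutes, and baseline vital signs are then recorded. Next, "the device will be re-applied and repeat vital signs will be obtained at 30- and 60-minute time periods". Finally, "a fourth set of vital signs will be obtained 30 minutes after device removal". Baseline, 30 minutes, 60 minutes and post-removal make four sets, so there is exactly one baseline set. The text mentions no replicate or averaged baseline.

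Table #1 states all five criteria as changes from baseline, for example "Respiration: > 20% increase in respirations per minute above baseline" and "Temperature: >0.6°F increase in temperature above baseline". It qualifies them: "Significant elevated stress is defined as persistence of any of the following in the absence of intrusive manipulations of the patient". It does not say how many readings, or how long a time, count as persistence.

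The endpoint is strict: "The primary endpoint of the study will be the absence of any device-related adverse events", and these include sustained vital-sign changes under Table #1. Phase 2 starts only if Phase 1 shows no specific negative findings. For Phase 2 the text says "After obtaining baseline vital signs prior to each session" and does not give the number of readings that make up a baseline.

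**The concern.** Persistence is meant to separate a real response from noise. It does that well for noise in the later readings, because two unrelated chance highs in a row are rare. It does it less well for noise in the baseline, because the same baseline is subtracted from both later readings. If the baseline was taken during quiet breathing or from a short count, both changes are inflated together. For oximetry, where the criterion is a fall, a chance high baseline has this effect.

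The endpoint is the absence of any device-related event in 25 infants, and there is no control group to show the background rate. A single false event therefore matters. It would either count against the device or be set aside as unrelated by a judgement for which the plan gives no rule. The decision to start Phase 2 would carry the same error.

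**Working it through.** **Plan's own figure.** There is none to reproduce. The documents give no within-infant variability, expected event rate or sample-size calculation.

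**Inputs from the plan.** One baseline set, two on-device readings (30 and 60 minutes), one post-removal set, a respiration limit of more than 20% above baseline, and 25 infants.

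**Assumptions.** No device effect. Persistent means both on-device readings over the limit. Readings are normal and independent around the infant's own level, with a within-infant coefficient of variation (CV) of 5, 10, 15 or 20%.

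**Step 1: one reading.** Scale the infant's true rate to 1. Let B be the mean of k baseline readings and X an on-device reading. The limit is crossed when D = X − 1.2B > 0.

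- Mean of D = −0.2; variance of D = CV² × (1 + 1.44/k).
- P(cross) = 1 − Φ(0.2 / (CV × √(1 + 1.44/k))).
- CV 10%, k = 1: 0.2/0.1562 = 1.28, so 10.0%.
- CV 10%, k = 3: 0.2/0.1217 = 1.64, so 5.0%.
- CV 10%, error-free baseline: 0.2/0.10 = 2.0, so 2.3%.

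**Step 2: both readings.** The two D values share B, so their correlation is (1.44/k)/(1 + 1.44/k), which is 0.59 for k = 1 and 0.32 for k = 3. If they were unrelated, the joint rate at CV 10% with k = 1 would be 0.10² = 1.0%. Simulation with 2 million draws gives 3.8%. The rate for either reading is 2 × P(cross) − P(both), for example 2 × 10.0 − 3.8 = 16.2%.

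| CV | Either, one baseline | Both, one baseline | Removed by persistence | Both, mean of three | Both, error-free baseline |
|---|---|---|---|---|---|
| 5% | 1.0% | 0.08% | 92% | about 0 | about 0 |
| 10% | 16.2% | 3.8% | 76% | 0.8% | 0.05% |
| 15% | 29.8% | 9.6% | 68% | 3.7% | 0.8% |
| 20% | 38.1% | 14.1% | 63% | 7.2% | 2.5% |

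The gap between the one-baseline and error-free columns is the part due to baseline error. At CV 10% it is nearly the whole rate.

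**Step 3: 25 infants.** Expected false events = 25p; chance of at least one = 1 − (1 − p)^25.

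| CV | Expected, one baseline | Expected, mean of three | At least one, one baseline | At least one, mean of three |
|---|---|---|---|---|
| 5% | 0.02 | about 0 | 2% | about 0 |
| 10% | 1.0 | 0.2 | 62% | 18% |
| 15% | 2.4 | 0.9 | 92% | 61% |
| 20% | 3.5 | 1.8 | 98% | 85% |

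**Step 4: correlated readings.** Take CV 10%, baseline readings 10 minutes apart, and correlation exp(−gap/τ). The chance of at least one false event then moves from 62% to 32% (τ = 10 minutes), from 57% to 40% (τ = 20), and stays at 26% (τ = 60).

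**Step 5: a true response.** With a true 30% rise and CV 10%, both readings cross the limit in 62% of infants with one baseline reading and 66% with three. At CV 20% the gain disappears.

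**Step 6: Phase 2 respiration.** Assume a mean of 50 breaths/min, an SD of 5 to 10, eight hourly readings and one baseline reading. Requiring all eight over the limit gives a false rate of 0.5% to 3.5% per session. Requiring any two in a row gives 12% to 33%. The result depends on the undefined meaning of persistence.

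**The case against.** A reader might infer that the persistence condition is useless, or that a low baseline makes every later reading look raised. Neither follows. In the same model persistence removes about 63% to 76% of chance exceedances at CVs of 10% to 20%. When the baseline is more than 1 SD low, both readings cross in only 22%, 46% and 60% of infants at CVs of 10, 15 and 20%.

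A reader might also infer that Phase 2 has the same single-reading baseline. The text does not say so, and the attached data collection sheet is not available here. What can be said is that the number of readings is unstated.

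The improvement from 62% to 18% is the most favourable of the three larger CVs and assumes independent readings. If a low baseline reflects a quiet state lasting an hour, averaging over 20 minutes gains almost nothing. If it reflects a short or poor count, averaging works well. This objection stands, and it limits what can be promised for the fix.

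The plan also has partial safeguards: events must be device-related, periods of intrusive handling are excluded, and there is a post-removal set. In the model 56% to 67% of false persistent events at CVs of 10% to 20% are still over the limit at that set, which would point away from the device. The plan does not say that the set is used this way, nor how attribution is made. The planned repeated-measures analysis does not change how an event is defined.

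**Conclusion.** The point holds for Phase 1. The numbering of the sets fixes one baseline set, every Table #1 criterion refers to it, and its error is common to both on-device changes. For respiration alone the false-event rate is negligible at a CV of 5% and reaches 3.8% to 14.1% per infant at CVs of 10% to 20%. At those CVs at least one false event in 25 infants is more likely than not if readings are independent. With slow drift the rate is lower (26% at CV 10% and τ = 60 minutes).

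These sizes rest on assumed CVs, normal readings and one interpretation of persistence. They are shown for respiration only and should not be carried over unchanged to the other four signs. The main gain from averaging is fewer false events. The gain in detecting a true response is small. This is a cheap improvement worth making, not a flaw that invalidates the study.

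**What to change.** In Phase 1, define baseline pulse, respiration and saturation as the mean of three bedside-monitor readings. Spread them as widely as practical over the later part of the existing 30-minute off-device interval, since wider spacing gives less correlated readings. Apply the existing Table #1 thresholds to that mean. Temperature and blood pressure may stay single to avoid extra handling; their baseline error then remains.

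State the same averaged baseline before each Phase 2 session, where the number of readings is not given. In the same edit, state how many readings count as persistence and whether the post-removal readings are used in attributing an event.

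The cost is a sentence or two of protocol text, two more data-sheet lines per baseline and a few minutes of nurse time. There is no extra handling if a monitor is already attached. The benefit depends on how strongly successive readings are correlated, which the documents do not tell us. The recorded replicates would provide an estimate.

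### Does a fit target of more than 90% of the target population ask more of 25 conveniently sampled infants than they can show?

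*Combined protocol and SAP*

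**What the plan says.** All the relevant text is in the Methods section of the combined protocol and SAP. The study is introduced as a "phased pilot study to evaluate patient tolerance and nursing ease-of-use". Phase 1 is a "60-minute initial size and fit evaluation of the device" on a "convenience sample of 25 infants admitted to the NICU". One of its two secondary endpoints is "NEATCAP sizing options able to fit >90% of the target population"; the other, in the same sentence, is a target of more than 80% positive answers on the staff questionnaire.

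The only analysis named is that the data "will undergo statistical analysis for repeated measures". That suits the vital signs but does not address a single proportion fitted. The baseline vital signs come after a step that begins "Once proper fit of the device has been assured"; the text does not say how an infant who cannot be fitted is counted. The move to the next phase is worded "If no specific negative findings are identified, Phase 2 will begin", with no mention of the fit target. Phase 2 lists no fit endpoint. The Risks/Benefits section gives the expected benefit as "critical data for the product development".

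**The concern.** The object of the endpoint is the target population, while the evidence is 25 infants chosen by convenience, with attending neonatologists free to advise against enrolment. If the endpoint were reported as met in its own words, a reader could take it that more than 90% of NICU infants can be fitted. A result that just passes, 23 of 25, is compatible with a true fit rate as low as 74.0%. Under exact 95% limits no possible result would establish the claim.

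The denominator raises a second worry. If infants who could not be fitted were replaced and left out of the count, the reported proportion would be too high. What is at stake is the conclusion about whether the size range is adequate, which matters for product development. The primary endpoint of device-related adverse events and the conduct of the trial are not affected.

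**Working it through.** **Inputs.** From Methods: n = 25 and a threshold of more than 90%. Not stated in the plan: confidence level, sidedness, method, definition of fit, denominator. The 95% and 90% levels below are assumptions. The plan gives no derivation of 25, so there is no stated calculation to reproduce.

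**1. Observed-rate reading.** 22/25 = 0.88 misses and 23/25 = 0.92 meets the target, so the benchmark is at least 23 fitted if 25 are attempted. The chance of meeting it is P(X ≥ 23) = Σ C(25,x) p^x (1−p)^(25−x) over x = 23, 24, 25.

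At p = 0.90 this is 300·0.90^23·0.10² + 25·0.90^24·0.10 + 0.90^25 = 0.266 + 0.199 + 0.072 = 0.537.

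| True fit rate | P(at least 23 of 25) |
|---|---|
| 80% | 9.8% |
| 85% | 25.4% |
| 90% | 53.7% |
| 95% | 87.3% |

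As a benchmark this is usable: it is usually missed at 80% and usually met at 95%. It does not prove that the true rate exceeds 90%.

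**2. Inferential reading, best possible result.** For x = n the exact lower limit is α^(1/n), the Wilson limit is n/(n + z²), and the one-sided mid-P limit is (2α)^(1/n). The Jeffreys limit is the lower quantile of a Beta(x + 0.5, n − x + 0.5) distribution.

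| Method, 25/25 | Lower limit | Above 90%? |
|---|---|---|
| Exact, two-sided 95%: 0.025^(1/25) | 86.3% | no |
| Exact, one-sided 95%: 0.05^(1/25) | 88.7% | no |
| Wilson, two-sided 95%: 25/(25 + 1.96²) | 86.7% | no |
| Wilson, one-sided 95%: 25/(25 + 1.645²) | 90.2% | yes |
| Jeffreys, two-sided 95% | 90.5% | yes |
| Jeffreys, one-sided 95% | 92.7% | yes |
| Mid-P, one-sided 95%: 0.10^(1/25) | 91.2% | yes |
| Exact, one-sided 90%: 0.10^(1/25) | 91.2% | yes |

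Whether a perfect result clears 90% therefore turns on a choice the plan never makes.

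**3. Anything less than perfect.** At 24/25 the exact 95% interval is 79.6% to 99.9%. The other lower limits checked are 80.5% (Wilson, two-sided 95%), 83.9% (Wilson, one-sided 95%), 82.8% (Jeffreys, two-sided 95%), 85.4% (Jeffreys, one-sided 95%) and 85.3% (exact, one-sided 90%). None reaches 90%. At 23/25 the exact 95% interval is 74.0% to 99.0%.

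**4. Would more infants help?** With every infant fitted, the exact limit first exceeds 90% when 0.90^n falls below α. One-sided 95% gives ln(0.05)/ln(0.90) = 28.43, so n = 29. Two-sided 95% gives ln(0.025)/ln(0.90) = 35.01, so n = 36. Neither number would cure convenience sampling, which limits generalisation whatever the interval.

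**5. Denominator.** Suppose, purely as an illustration, that 28 infants were tried and 25 fitted: 25/28 = 89.3% misses, while dropping the 3 failures gives 25/25 = 100%. The text gives no sign that this is intended. It speaks of 25 infants and mentions neither replacement nor exclusion of those who cannot be fitted. In a size-and-fit evaluation a failed fitting is itself the outcome, so the ordinary count includes it.

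**The case for a change.** The strongest case for a change is that the wording is literally a population statement, that Phase 1 is the only planned source of evidence for it, and that one sentence would settle the meaning, the interval and the count. Pilot status explains a small sample but does not make a population claim supportable. The denominator question also arises under a purely descriptive reading.

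Much of this is correct. The exact limits are right, a pass at 23 of 25 is weak evidence about the population, and a final report should not repeat the endpoint's words as a finding. But the exact 95% standard is brought in from outside. The questionnaire target in the same sentence has the same form, and both read most easily as design benchmarks. The denominator worry needs an unusual counting choice that nothing in the text suggests, and the protocol refers to an attached data collection sheet, not available here, which may record fit or size.

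A rewritten rule would need care too. A fixed count of 23 is right only if exactly 25 are attempted; with 28 attempts the target needs 26 (26/28 = 92.9%). Applying the percentage to whatever number was attempted is what the present threshold already allows.

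**Conclusion.** No change to the plan is needed. The endpoint is loosely worded, but taken as an observed benchmark in a pilot it can be applied as it stands: count the infants fitted among those tried and compare the proportion with 90%. The missing pieces (interval, definition of fit, treatment of failed fittings) are details that a competent analyst supplies at reporting. The sensible choices are clear: failures stay in the denominator, an interval accompanies the proportion, and no statement is made that fit in all NICU infants exceeds 90%.

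The size of the issue is limited to how firmly adequate sizing may be asserted. At the lowest pass the exact 95% interval runs from 74.0% to 99.0%; at a perfect score the lower limit lies between 86.3% and 92.7% across the methods examined. Enrolment, safety assessment and the stated condition for starting Phase 2 would be the same with or without new wording.

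This conclusion rests on two assumptions: that the target is meant descriptively, as the pilot setting suggests, and that infants who cannot be fitted are counted as such. If the sponsor meant to use Phase 1 as formal proof of population fit above 90%, the concern would stand, but nothing in the documents sets out such a test.
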